### 9.4. Subject Status and Classification

A subject will be considered enrolled in this study at the time of the study-specific informed consent form (ICF) execution.

#### 9.5. Enrollment Controls

The study will implement a formal *Enrollment Communication Plan*. The plan will outline the specific activities, as well as the nature and timing of communications to investigators in order to minimize the risk of enrollment beyond the protocol-specified enrollment caps determined by the statistical analysis plan.

### 9.6. End-of-Study Definition

The study is considered complete when the last subject's last study visit has occurred.

### 9.7. End of Study Action Plan

[figure not shown]

# 10. Study Methods

### 10.1. Data Collection

The data collection schedule is shown in Table 10.1 1.

#### 10.2. Study Candidate Screening

Enrolled subjects will be screened for participation in the study based on study Inclusion/Exclusion criteria as listed in Section 8. Subjects who have provided informed consent and who have been determined to not meet all eligibility requirements will be withdrawn.

### 10.3. Informed Consent

Written informed consent must be obtained from all potential study candidates. A subject is considered enrolled only after the subject signs and dates the ICF.

- Subjects will be asked to sign the ICF before any study-specific tests or procedures are performed;
- The context of the study must be fully explained, and the subjects must be given the time and opportunity to ask questions and have those questions answered to their satisfaction;
- Study personnel should explain that even if a subject agrees to participate in the study and signs an ICF, certain screening procedures might demonstrate that the subject is not eligible to continue participation;
- The ICF is study specific and must be approved by the Ethics Committee (EC) and the sponsor.
- Written informed consent must be recorded appropriately by means of the subject's dated signature.

Participants are required to be on stable anti-parkinsonian medications for 28 days prior to informed consent.

### 10.4. Screening Period/Baseline Visit (up to 45 days post informed consent)

During the screening period, subjects will undergo screening procedures as listed in Section 8 to determine their eligibility in the study. Subjects may have multiple visits to the neurologist and/or neurosurgeon for this purpose.

Subjects are required to be on stable anti-parkinsonian medications for 28 days prior to informed consent. Those subjects who meet all inclusion criteria and none of the exclusion criteria may continue participation in the study.

The Baseline Visit may occur anytime within the screening period and will serve as the final determination of eligibility in the study. It is recommended that *meds off/meds on* assessments be completed at the Baseline Visit.

10.6. Device Activation - Day 0

The Vercise™ DBS System will be activated following completion of the system implant and this visit will be considered Day 0 for the study.

Subjects will be asked about any adverse events since their last study visit. Any changes to subjects' anti-parkinsonian medications will be documented.

The device stimulation parameters will be chosen based on subject and physician preference. Subjects will be instructed on the use of the remote control and charging system. Any precautions/restrictions will be discussed.

Initial programming will be completed, and information related to efficacy, side-effect thresholds and programming parameters may be collected. It is recommended that the initial programming be done in the *meds off* condition. If GUIDE XT is used for planning purposes, additional information may be collected.

Subjects may return to the clinic for optimization of stimulation parameters as needed.

### 10.7. Week 10 Visit post-activation (+ 7 days)

Subjects will return to the clinic for optimization of stimulation parameters and any adverse events since their last study visit will be collected.

#### Prior to Week 12 Visit:

Subjects must discontinue taking their anti-parkinsonian medications for at least 12 hours (or overnight) prior to the visit. Additionally, long acting anti-parkinsonian medications may be withdrawn for 24 hours prior to visit.

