### 6.1. Primary Endpoint

[figure not shown]
Mean change in MDS-UPDRS III scores from Baseline in *meds off* condition to 12 weeks post device-activation in *stim on/meds off* condition.

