# 7. Study Design

The study is a prospective, multi-center, open label confirmatory study. The Cartesia eXTend 3D study meets all the requirements of a confirmatory study per ISO 14155 Annex I.

Subjects will receive the VerciseTM CartesiaTM (X/HX) 16-contact Directional Lead with the VerciseTM GenusTM DBS System and will be followed per study schedule as shown in Figure 2.2 below.

[figure not shown]

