## 10.8. Week 12 Visit post-activation (+ 7 days)

At Week 12 Visit post-activation, subjects will return to the clinic in the stim on/meds off condition.

Any adverse events since the last study visit will be collected. Any changes to subjects' antiparkinsonian medications will be documented. Only upon completion of study related assessments, subjects' device may be programmed or further optimized as needed.

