## 11.1.1. Hypotheses

The primary statistical hypothesis in this study is that the mean change in MDS-UPDRS III scores from Baseline in *meds off* condition to 12 weeks post device-activation in *stim on/meds off* condition is greater than 5 (MCID). More specifically,

$$H_0$$
:  $\mu_B - \mu_{12} \le 5$ 

$$H_1$$
:  $\mu_B - \mu_{12} > 5$ 

Where  $\mu_B$  and  $\mu_{12}$  is the mean MDS-UPDRS III scores in *meds off* condition at Baseline and at 12 weeks post device-activation respectively.

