#### 11.2. General Statistical Methods

#### 11.2.1. Analysis Sets

The following sets will be analyzed.

- Intent-to-Treat (ITT) Population: All subjects in which implantation of the device is attempted (successful or not), will be included in the ITT population. This will be the primary analysis set.
- Per Protocol (PP) Population: All subjects who receive the study device, with no major protocol deviations.
- Safety Population: All subjects who sign the IRB-approved written Informed Consent form

Subjects who have been withdrawn due to an explant or loss of treatment inefficacy will be analyzed as treatment withdrawals, while all other withdrawals will be considered as study withdrawals.

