## 11.2.4. Data Analyses

All statistical analyses will be done using the SAS System software, version 8.2 or later (Copyright © 2000 SAS Institute Inc., [name]. All rights reserved). Additional details on these analyses can be found in the Statistical Analysis Plan.

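### Does the optional 24-hour withdrawal of long-acting drugs before Week 12 undermine the meds-off comparison with baseline?

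*Combined protocol and SAP*

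**What the plan says.** The primary endpoint (section 6.1) is: "Mean change in MDS-UPDRS III scores from Baseline in *meds off* condition to 12 weeks post device-activation in *stim on/meds off* condition". Section 11.1.1 tests whether the mean improvement exceeds 5 points, where each of the two means "is the mean MDS-UPDRS III scores in *meds off* condition at Baseline and at 12 weeks post device-activation respectively". Both ends of the change score are therefore meant to be measured off medication.

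The instructions headed Prior to Week 12 Visit have two parts of different force. Stopping anti-parkinsonian drugs for at least 12 hours, or overnight, is mandatory. The further step is permissive: "Additionally, long acting anti-parkinsonian medications may be withdrawn for 24 hours prior to visit". The text does not say who decides, on what criterion, or whether the choice is recorded.

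For baseline, section 10.4 only recommends that the meds-off and meds-on assessments be done at the Baseline Visit. The public text then goes straight to section 10.6. Section 10.1 says "The data collection schedule is shown in Table 10.1 1", but that schedule is not shown. The eligibility tables in section 8 are also not shown, the numbering passes from 11.2.2 to 11.2.4, and section 11.2.4 defers to a document that is not reproduced: "Additional details on these analyses can be found in the Statistical Analysis Plan".

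At Week 12 (section 10.8), "Any changes to subjects' antiparkinsonian medications will be documented". The Per Protocol set (section 11.2.1) is "All subjects who receive the study device, with no major protocol deviations".

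**The concern.** A change score is interpretable only if meds off means the same thing at both ends. On the published wording, a fully compliant subject could be assessed at Week 12 with a long-acting drug still acting after having withheld it before baseline, or the reverse. Residual drug at Week 12 would be counted as a stimulation effect and overstate the change. Residual drug at baseline would understate it.

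The published safeguards do not clearly catch this:

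- The 28-day stability requirement (sections 10.3 and 10.4) concerns the regimen before consent, not preparation for an off assessment.
- Documenting medication changes is not the same as recording the last dose before an assessment.
- Using or declining an option is not a deviation, so the Per Protocol set would keep mismatched subjects.
- Section 18.5 expects medication to be adjusted once stimulation starts, so regimens can differ between the two visits.

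Section 7 states: "The study is a prospective, multi-center, open label confirmatory study". No control arm is described, so a systematic mismatch would not cancel against a comparison group. At stake are the size and precision of the reported change and, if the true effect were close to the margin, the error rate of the test.

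**Working it through.** The published text gives no sample size, alpha or planning effect, so there is no figure of the plan's own to reproduce. The calculation below only sets a scale.

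**Inputs from the protocol.** Margin 5 (section 11.1.1). Earlier study: mean change 23.8, with 10.6 read as the SD (section 4.1). That result is at 6 months and is not stated as a planning value for this trial.

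**Assumed inputs.** Fraction of subjects mismatched p = 0.10 to 0.30. Residual drug difference d = 3 to 8 points. One-sided alpha 0.025. n = 10 or 20. The documents support none of these.

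**One-way mismatch.** Shift in the mean = p × d.
- Smallest: 0.10 × 3 = 0.3 points, and 0.3 / 23.8 = 1.3%.
- Largest: 0.30 × 8 = 2.4 points, and 2.4 / 23.8 = 10.1%.

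**Balanced mismatch** (half in each direction). The mean does not move. SD = √(10.6² + p × d²).
- Smallest: √(112.36 + 0.9) = 10.64, variance up 0.8%.
- Largest: √(112.36 + 19.2) = 11.47, variance up 17.1%. Equal precision would need about 17% more subjects.

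**Power of a one-sample t test against 5** (noncentral t, noncentrality = (mean − 5) / SD × √n).

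| Case | Mean | SD | n = 10 | n = 20 |
|---|---|---|---|---|
| No mismatch | 23.8 | 10.6 | 99.86% | >99.9% |
| Largest shift, understating | 21.4 | 11.22 | 98.34% | >99.9% |
| Largest balanced mismatch | 23.8 | 11.47 | 99.56% | >99.9% |

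In the second row the SD is √(112.36 + 0.3 × 0.7 × 64) = 11.22, because a one-way mismatch in 30% of subjects also adds variance.

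**Distance to the margin.** 23.8 − 5 = 18.8 points, which is 18.8 / 10.6 = 1.77 SD and 18.8 / 2.4 = 7.8 times the largest assumed shift.

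**Unfavourable corner.** If the true change were exactly 5, with n = 20 and SD 10.6, an overstating shift of 1, 2 or 3 points would raise the one-sided error from 0.025 to 0.060, 0.123 or 0.224. This requires a true effect 18.8 points below the earlier result.

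**Reading the passages together.** A mandatory minimum for all drugs plus permission for a longer withdrawal of some is internally coherent. No published passage contradicts it. What cannot be checked is how it relates to the baseline preparation, because that wording is not in the public version.

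**The case for a change.** The strongest case for acting is that the Week 12 instruction is published and permissive. Even if the baseline text repeats it word for word, two identical options still allow two different choices for one subject. Only a rule that ties the visits together would close that gap. The study exists to document outcomes, so the estimate matters as well as the test. If last-dose times were not captured, they may not be recoverable, and capturing them costs little.

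Part of this stands. The published text does leave the link open, and matched preparation would make the change score cleaner. Three things keep it from becoming a required change.

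- The half of the comparison that would settle the matter is text that is not shown. The case report form is not shown either, so a recording gap is presumed rather than seen.
- Requiring the same handling at both visits would turn discretion over drug withdrawal into an obligation. That is clinical management, and no published passages conflict on it. Section 18.4 lists discomfort during off-medication testing among the risks of participation, which makes some discretion understandable.
- A matching rule would not fully remove the problem. If a long-acting drug is started, stopped or changed in dose after baseline, the same choice can still leave different residual drug. An analysis limited to matched subjects would select on a post-baseline feature and could be biased itself, so it could only be supportive.

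**Conclusion.** The concern does not call for a change to the plan. It correctly observes that the long-acting step before Week 12 is optional and that no published passage links it to baseline. It does not show that the plan lacks such a link, because the baseline preparation, the visit schedule and the analysis detail are not in the public text.

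The possible effect has no known direction. Under assumed inputs it is a shift of 0.3 to 2.4 points in the mean, or an SD of 10.64 to 11.47 in place of 10.6. The test against 5 is safe if the true change is near 23.8 points: power is at least 98.3% at an assumed n = 10 and above 99.9% at n = 20. That assurance rests on the earlier study's result carrying over to this device and time point. It would not hold for a true change close to the margin.

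What is left is a low-severity clarification. The sponsor can be asked how the Week 12 wording fits with the baseline preparation, and whether the last dose and its time are recorded at both assessments. An analyst with those data could describe the off states in a supportive display, with the ITT analysis unchanged.

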## 10.8. Week 12 Visit post-activation (+ 7 days)

At Week 12 Visit post-activation, subjects will return to the clinic in the stim on/meds off condition.

Any adverse events since the last study visit will be collected. Any changes to subjects' antiparkinsonian medications will be documented. Only upon completion of study related assessments, subjects' device may be programmed or further optimized as needed.

### 10.9. Week 26 Visit post-activation (± 21 days)

At Week 26 Visit post-activation, subjects will return to the clinic in the stim on/meds off condition.

Any adverse events since the last study visit will be collected. Any changes to subjects' antiparkinsonian medications will be documented. Only upon completion of study related assessments, subjects' device may be programmed or further optimized as needed.

# 10.10. Years 1, 2, 3, 4 and 5 Visit post-activation ( $\pm$ 45 days)

Subjects will return to the clinic in the stim on/meds off condition at these annual visits.

Any adverse events since the last study visit will be collected. Any changes to subjects' antiparkinsonian medications will be documented. Only upon completion of study related assessments, subjects' device may be programmed or further optimized as needed.

# 10.11. Replacements/Revisions

It is possible that leads may be placed incorrectly, migrate, fail or get infected. This may require repositioning, replacement or explant. It is also possible that the IPG may fail and require replacement or explant, or need repositioning due to migration, discomfort, etc. The decision to reposition or replace any device component will be made by the investigator along with the subject. Site staff should notify BSC before the procedure. Subjects not agreeing to a recommended lead revision will be withdrawn from the study but will be included in the intent-to-treat and safety analyses. Subjects agreeing to lead revision will continue on study and will be followed according to the study schedule. Effectiveness data from these subjects will be included in the intent-to-treat analysis. Any replacements, revisions or explants performed during the course of the study should be recorded in the electronic database. Subjects who are not willing to an IPG revision will only be withdrawn, per investigator discretion, if the performance of the device has been compromised e.g. unable to charge due to migration.

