### 4. Introduction

### 4.1. Background

Parkinson's disease (PD) is a progressive neurodegenerative disorder that affects 5.2 million people worldwide [4]. The prevalence of PD is estimated at 0.3% of the overall population in industrialized countries and advances to 1% by age 60 and 4% in the highest age group [5]. The hallmark signs of PD include movement disorders such as bradykinesia, resting tremors, and muscle rigidity[6].

The motor symptoms of PD are associated with a dopamine deficiency resulting from the degradation of dopaminergic neurons in the substantia nigra pars compacta (SNc). At present there is no cure for PD; treatment is focused on medical management of motor symptoms. Medical therapy has been primarily focused on restoring dopamine levels through the administration of levodopa, dopamine agonists, or monoamine oxidase B inhibitors. Current standards for patient care recommend levodopa as first line of therapy for the symptomatic control during the early, uncomplicated stages of PD [7, 8]. Unfortunately, chronic treatment with levodopa frequently leads to significant side effects, especially dyskinesias and motor fluctuations [9].

Previously, for subjects who had reduced response to medical therapy, pallidotomy (destruction of the globus pallidus) and thalamotomy (destruction of the thalamus) were the only available treatment options. In the 1990s, high-frequency deep brain stimulation (DBS) was demonstrated to be effective in reducing the motor complications of subjects with PD [10]. Since that time, numerous case studies and trials have substantiated these early findings. In addition, six recent large, multicenter, randomized trials have demonstrated the effectiveness of the therapy [11-17].

Timmermann et al. published the results of Boston Scientific sponsored VANTAGE Study: a non-randomized, prospective, multicenter open-label study where 40 idiopathic PD patients at 6 European centers received bilateral STN DBS with VerciseTM DBS System [18]. The study successfully achieved its primary endpoint (p < 0.0001) and reported a mean difference of  $23.8 \pm 10.6$  points in MDS-UPDRS III scores in the stim ON/meds OFF condition at 6 months after implantation compared with Baseline.

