#### 9.2. Withdrawal

All subjects enrolled in the clinical study (including those withdrawn from the clinical study) shall be accounted for and documented. If a subject withdraws from the clinical investigation, the reason(s) shall be reported. If such withdrawal is due to problems related to

investigational device safety or performance, the investigator shall ask for the subject's permission to follow his/her status/condition outside of the clinical study.

Reasons for withdrawal include but are not limited to:

- Loss of treatment efficacy
- Adverse events,
- physician discretion,
- subject choice to withdraw consent,
- subject's failure to meet the study's eligibility criteria after enrollment but prior to system implant,
- failure to receive the BSC DBS system,
- lost to follow-up,
- pregnancy\*,
- death,
- explant of the entire DBS system\*\*

While study withdrawal is discouraged, subjects may withdraw from the study at any time, with or without reason, and without prejudice to further treatment.

All applicable case report forms (CRFs) up to the point of subject withdrawal and an "End of Study" form must be completed. Any subject deemed "lost to follow-up" should have a minimum of three documented attempts to contact him/her prior to completion of the "End of Study" form.

Additional study data may no longer be collected after the point at which a subject has been withdrawn from the study or withdraws consent, for whatever reason. Data collected up to the point of subject withdrawal may be used. Subjects withdrawn after completing the implant procedure will not be replaced and will be included in the site's overall total for activated subjects.

- \*Women who become pregnant during the study, will be withdrawn and their device deactivated.
- \*\*If the entire DBS system of a study subject was explanted, it is recommended to follow the subject for 30 days after the explant of the system.

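### Subjects who decline a recommended lead revision before Week 12 stay in the ITT set, but protocol rules leave them without a primary endpoint score

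*Combined protocol and SAP*

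**What the plan says.** Section 10.11 recognises that revision may become necessary: "It is possible that leads may be placed incorrectly, migrate, fail or get infected". It then sets different rules by the subject's decision.

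- **Declines a lead revision:** "Subjects not agreeing to a recommended lead revision will be withdrawn from the study but will be included in the intent-to-treat" and safety analyses.
- **Accepts a lead revision:** continues on the study schedule, and "Effectiveness data from these subjects will be included in the intent-to-treat analysis".
- **Declines an IPG revision:** "will only be withdrawn, per investigator discretion, if the performance of the device has been compromised"; a device that cannot be charged is the example given.

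Section 9.2 fixes what withdrawal means for data: "Additional study data may no longer be collected after the point at which a subject has been withdrawn from the study", for any reason. Data obtained before withdrawal may be used, and implanted subjects are not replaced. After withdrawal for a device safety or performance problem, the investigator asks permission to follow the subject, but outside the study.

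Section 11.2.1 defines the primary analysis set by attempted implantation: "All subjects in which implantation of the device is attempted (successful or not), will be included in the ITT population". Section 11.1 makes the primary endpoint the change from Baseline (meds off) to 12 weeks after activation (stim on/meds off), tested against a margin of 5 points. On analysis detail, Section 11.2.4 says: "Additional details on these analyses can be found in the Statistical Analysis Plan".

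**The concern.** Declining further surgery is not the same as declining study visits, but Section 10.11 turns the first into the second. Among subjects with a lead problem before Week 12, the primary score is observed in those who accept revision and not in those who decline.

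This loss is unlikely to be random. Section 18.1 lists poor initial lead location as a possible cause of ineffective therapy or surgical revision, so some of the missing scores would probably be poor ones. That is not always so: Section 10.11 also names infection, which need not go with a poor motor score.

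The study has a single arm and its stated purpose is to document effectiveness. The size of the mean change is therefore a main result, and there is no control group in which a similar loss could offset the bias.

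**Working it through.** **Document logic.** The plan states no figure on this point, so there is none to reproduce. The chain is:

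1. Implantation attempted, so the subject is in ITT, the primary set (11.2.1).
2. Lead revision recommended before Week 12 and declined, so the subject is withdrawn but kept in ITT (10.11). Subjects withdrawn after declining an IPG revision are also in ITT, by step 1.
3. Withdrawn, so no further study data (9.2).
4. The primary endpoint needs a Week 12 score (11.1), so the subject has a Baseline value and no endpoint value.

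No visible passage allows a Week 12 assessment after withdrawal. Subjects withdrawn after Week 12 keep their primary score and are not affected.

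**Bias if the missing scores are left out.** Overstatement = f × p × (m − c), where

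- f = share of the ITT set withdrawn this way before Week 12 (assumed);
- p = share of those who respond poorly, the rest being like the observed subjects (assumed);
- c = mean change in the poor responders (assumed);
- m = 23.8, from Section 4.1, where VANTAGE reports 23.8 ± 10.6 "points in MDS-UPDRS III scores in the stim ON/meds OFF condition at 6 months after implantation compared with Baseline".

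| f | c | p = 100% | p = 50% | p = 25% | p = 0 |
|---|---|---|---|---|---|
| 2.5% | 0 | 0.60 | 0.30 | 0.15 | 0 |
| 5% | 0 | 1.19 | 0.60 | 0.30 | 0 |
| 2.5% | 10 | 0.35 | | | |
| 5% | 10 | 0.69 | | | |

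For example, 0.05 × 1 × (23.8 − 0) = 1.19 points. The sign reverses if those lost had done better than average.

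**Effect on the confidence limit.** The sample size is not in the public text, so n = 40 is assumed. Let k subjects have zero change and the other n − k have mean 23.8 and SD 10.6. Then mean = (n − k) × 23.8 / n, and

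SD² = [(n − k − 1) × 10.6² + (n − k) × 23.8² − n × mean²] / (n − 1).

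The lower limit is two-sided 95%, from the t distribution on n − 1 degrees of freedom.

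| n | k | Mean | SD | Lower limit |
|---|---|---|---|---|
| 40 | 0 | 23.80 | 10.60 | 20.41 |
| 40 | 1 | 23.21 | 11.12 | 19.65 |
| 40 | 2 | 22.61 | 11.58 | 18.91 |
| 20 | 1 | 22.61 | 11.61 | 17.18 |
| 80 | 4 | 22.61 | 11.57 | 20.03 |

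All lower limits are far above 5.

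**When the verdict could differ.** Assume a one-sided 0.025 t-test against 5 with SD 10.6. The lower end of the window is the smallest observed mean that passes on n − k subjects. The upper end is the smallest that still passes once k zero-change subjects are added.

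- n = 40, k = 1: 8.44 to 8.59.
- n = 40, k = 2: 8.48 to 8.80.
- n = 20, k = 1: 10.11 to 10.48.

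With standard error 10.6/√(n − k), the upper ends lie 9.0, 8.7 and 5.5 standard errors below 23.8.

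**The case against.** The strongest reply is that no harm is shown. The documents give no value for f, p or c. The top of the range needs 5% of subjects lost, all of them poor responders with no improvement at all, and that amounts to two subjects in an assumed 40. The VANTAGE scale is also borrowed: it was bilateral STN stimulation at 6 months after implantation, whereas the planned indication here includes unilateral and GPi use and the endpoint is 12 weeks after activation. All of this stands, and it limits the point to a small one.

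Second, the analysis may already deal with these subjects. The SAP detail and Section 11.2.3 are not in the visible text, and 11.2.1 separates treatment withdrawals from study withdrawals. A conservative rule would remove the overstatement. This also stands. But the visible text does not say how either class enters the primary analysis, and an imputation rule can only model the missing score.

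Third, the passages do not contradict each other: ITT membership does not require a Week 12 score. That is right. This is a design choice that could be improved, not an inconsistency.

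Fourth, Section 9.2 stops data for other reasons too, and loss of efficacy is tied even more directly to poor response. That is fair. What sets decliners apart is that Section 10.11 itself imposes the withdrawal on someone who may be willing to attend. The point does argue for a sensitivity analysis wider than decliners alone.

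**Conclusion.** The concern holds. By stated rule, a subject who declines a lead revision and is withdrawn before Week 12 is in the primary analysis set without a primary score. The same applies to a subject withdrawn at the investigator's discretion after declining an IPG revision.

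The consequence is modest: about 0 to 1.2 points of overstatement on a 23.8-point improvement, if 2.5% to 5% are lost, their scores are left out and they did no better than the observed subjects. It affects the accuracy of the estimate. The pass/fail result against 5 points would not change at a VANTAGE-sized effect. Confidence is medium, because the number affected and the missing-data rule are both unknown. This is a cheap improvement and not a flaw that threatens the study.

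**What to change.** Align Sections 10.11 and 9.2 with the ITT definition, so that declining a lead or IPG revision does not by itself end study data collection. Where the subject still consents and it is feasible, collect the scheduled Week 12 MDS-UPDRS III, record whether stimulation was on, and collect adverse events. Later visits can be optional. Data collection under Section 9.2 can stay as it is for all other withdrawal reasons.

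Unless the SAP already does so, state how a score taken with stimulation off is used. Also add a sensitivity analysis that assigns no change from Baseline to decliners still without a Week 12 score. Extending it to every withdrawal before Week 12 would answer the wider objection. Nothing here bears on whether a lead or IPG should be revised or how a device should be managed.

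**Cost.**

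- A protocol amendment with EC review (Section 16.3) across up to 15 sites, and possibly a revised consent form.
- For a few subjects, one visit off medication, with the discomfort and fall risk named in Section 18.4. The full schedule would be up to seven such visits (Week 12, Week 26 and Years 1 to 5), which is not asked for.
- Some stim-on scores will remain unobtainable, for example where the device cannot be charged, so some primary values will still be missing.
- One extra analysis if none exists, and possibly a less favourable mean.
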